9.1. Adverse Events

All AE summaries will be restricted to treatment-emergent AEs (TEAEs) only. A TEAE is defined as any event not present before exposure to study drug or any event already present that worsens in either intensity or frequency after exposure to study drug.

For the purpose of inclusion in TEAE tables, incomplete AE start and end dates will be imputed as follows:

Missing onset dates (where UK and UNK indicate unknown or missing day and month respectively):

- UK-MMM-YYYY: If the month and year are different from the month and year of the date of first dose, assume 01-MMM-YYYY. If the month and year are the same as the month and year for the date of first dose, and the end date (after any imputation) is on or after the date of first dose, then assume the date of first dose. If the month and year are the same as the date of first dose, and the end date (after any imputation) is prior to the date of first dose, then assume the end date for the start date.
- DD-UNK-YYYY/UK-UNK-YYYY: If the year is different from the year of the date of first dose, assume 01-JAN-YYYY of the collected year. If the year is the same as the date of first dose year, and the end date (after any imputation) is on or after the date of first dose, then assume the date of first dose. If the year is the same as the date of first dose, and the end date (after any imputation) is prior to the date of first dose, then assume the end date for the start date.

Missing end dates (where UK and UNK indicate unknown or missing day and month respectively):

- UK-MMM-YYYY: Assume the last day of the month;
- DD-UNK-YYYY/UK-UNK-YYYY: Assume 31-DEC-YYYY.

All adverse events will be classified by SOC and PT according to the Medical Dictionary for Regulatory Activities (MedDRA, Version 19.1 or higher).

An overview summary of the number and percentage of subjects with any TEAE, serious TEAE, treatment-related TEAE, treatment-related serious TEAE, TEAE leading to study treatment discontinuation, TEAE leading to study discontinuation, and AE leading to death will be provided by treatment group.

All AEs will be presented in a listing.

9.1.1. Treatment-Emergent Adverse Events

Summaries of the total number of TEAEs and the number and percentage of subjects with at least one TEAE will be provided by treatment. Treatment-emergent AEs will be presented by SOC and PT. At each level of subject summarization, a subject is counted once if the subject reported one or more events. Percentages will be calculated out of the number of subjects in the safety set.

The summary of TEAEs will be presented in alphabetical order of SOC. Within each SOC, PTs will be sorted in descending order from the PT with the highest total frequency (that is, summed across all treatment groups) to the PT with the lowest total frequency. If the total frequency for any two or more PTs is equal, the PTs will be presented in alphabetical order.

The summarization described above will also be repeated for the following:

- Serious Adverse Events;
- Treatment-Related Adverse Events;
- Treatment-Related Serious Adverse Events;
- Adverse Events Leading to Dose Interruption.

The adverse events with a missing relationship will be considered as “Treatment Related” in the tables.

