11.4 Early Termination

With effective oral therapy, immediate relief of all symptoms is not expected and subjects should not expect immediate relief.

If the subject experiences persistence or worsening or recurrence of symptoms that per the investigator's assessment (e.g., symptoms ≥ 3) warrant the use of rescue antifungal therapy, a vaginal examination with investigator's rating of signs should be completed. Additionally, vulvovaginal samples should be obtained for KOH testing and pH measurements by the local laboratory, fungal culture by the central laboratory and investigation of other pathogens such as bacterial vaginosis and *Trichomonas vaginalis* by the local laboratory.

If the KOH test is negative, the investigator should consider other causes for the persistence or worsening of the symptoms as antifungal rescue medication may not be indicated.

If the investigator's rating of the vulvovaginal signs and vaginal sample collection is not possible prior to the initiation of the rescue therapy, it should still be completed as soon as possible after rescue therapy is initiated.

In addition to the vaginal examination, the symptoms that led to the use of rescue antifungal therapy should be documented in the eCRF and the following procedures should also be completed:

- If rescue therapy is administered prior to or at the TOC visit, all TOC visit procedures should be completed and no additional visits will be needed. The subject will be considered as early termination due to lack of efficacy prior to or at TOC.
- If rescue therapy is administered after the TOC visit but prior to or at the FU visit, all FU visit procedures should be completed and no additional visits will be needed. The subject will be considered as early termination due to lack of efficacy after TOC but prior to or at FU.

Oral fluconazole [one 150-mg dose] may be provided to study sites as rescue medication. However, at the investigator's discretion other approved antifungal agent may be administered as rescue medication to a particular patient for whom fluconazole is not considered the optimal option. All rescue antifungal medications should be documented in the eCRF.

Details of study treatment groups and dietary requirements for treatment administration are provided in [Section 12.1](#) and [Section 12.2](#), respectively.

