16.9 Adverse Event Collection Timeframe

All AEs and SAEs will be recorded from the time informed consent is obtained through the FU visit (end of study).

All AEs reported by the subject or observed by members of the clinical staff will be evaluated by the principal investigator (PI) or qualified designee. The PI will attempt, if possible, to establish a diagnosis based on presenting signs and symptoms. The nature of the AE, time of onset relative to study drug administration, duration, severity, and relationship to treatment should be determined. Details of any corrective treatment must be recorded in the eCRF. The PI will determine whether any changes have occurred in baseline signs and symptoms. All AEs and SAEs will be collected in the eCRF.

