3.1. Overall Study Design and Plan

This is a Phase 3, randomized, multicenter, double-blind, placebo-controlled study to evaluate the efficacy and safety of oral ibrexafungerp compared to placebo in female subjects 12 years and older with AVVC.

Approximately 366 eligible subjects will be enrolled and randomized in a 2:1 ratio to either ibrexafungerp (300-mg dose twice a day [BID]) or matching placebo administered BID for 1 day. The primary objective of this study is to evaluate the efficacy of oral ibrexafungerp in subjects with AVVC by comparing the clinical outcomes of ibrexafungerp and placebo.

The study will consist of a Screening visit, a Baseline visit on Day 1 (these visits may occur on the same day), a TOC visit on Day 11 (± 3) and a FU visit on Day 25 (± 4).

The schedule of study assessments is presented in [Appendix 1](#).

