5.1. Disposition

A disposition of subjects includes the number and percentage of subjects for the following categories: subjects in each analysis set (ITT, mITT, PP, SS), subjects who completed TOC visit, subjects who completed the study (without need for antifungal treatment), subjects who completed the study (with need for antifungal treatment at FU visit), subjects who discontinued from the study, and the reasons for study discontinuation will be presented by the ITT and mITT sets. All percentages will be based on the number of subjects in each corresponding set.

The reason for study discontinuation may include any of the following: lack of efficacy and/or use of antifungal therapy prior to TOC; use of antifungal therapy after TOC (but prior to FU visit); adverse event; lack of efficacy after TOC; lost to follow-up; physician decision; pregnancy; study terminated by sponsor; study subject withdrawal by parent or guardian; withdrawal by subject; other; death, and trial screen failure.

Subject disposition data will be presented in a listing.

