7.2.1. Study Participation Calculation and Extent of Exposure

The duration of study treatment (hours) is calculated as (the date time of the second dose – the date time of the first dose + 1) / 3600 only for subjects who got both 2 study treatments. For subjects who only got 1 or none study treatment, the duration of study treatment will be missing.

The duration of study participation (days) is calculated as date of Study Completion/Termination recorded on the End of Study page – first dose date + 1. If the date of Study Completion/Termination on the End of Study page is missing, or if a subject is lost to follow-up, the latest available visit date will be used.

The cumulative doses taken across the treatment period is defined as the number of study drug dispensed minus the number of study drug returned. If the study drug bottle was not returned, the dose diary data will be considered for the cumulative dose calculation. When subject answered no dose missing, we can assume the cumulative dose is 4. When subject answered only 1 dose missing, we can assume the cumulative dose is 2. When subject answered 2 doses missing, we can assume the cumulative dose is 0 tablet. The cumulative dose is missing when subject didn't answer at least one missing dose question.

The duration of study participation, the number of drug administrations and the cumulative actual doses by treatment will be summarized by summary statistics.

All this exposure information will be presented in a listing.

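### Women rescued by TOC are observed for adverse events for less time, probably more often on placebo, yet TEAE percentages use the whole safety set; the distortion is probably small, and a TEAE table limited to the period up to TOC is a cheap improvement

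*SAP*

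**What the plan says.** - **When visits stop.** Under Protocol 11.4, for a woman rescued before or at TOC, "all TOC visit procedures should be completed and no additional visits will be needed". Her status is fixed as well: "The subject will be considered as early termination due to lack of efficacy prior to or at TOC". SAP 5.1 lists among the reasons for study discontinuation "lack of efficacy and/or use of antifungal therapy prior to TOC".
- **How long adverse events are collected.** Protocol 16.9 runs collection from consent to the FU visit, which it equates with the end of the study. SAP 3.1 places "a TOC visit on Day 11" (3 days either side) and FU on Day 25 (4 days either side).
- **Who is counted.** The safety set (SAP 4.3) needs one dose and one post-baseline evaluation, so a rescued woman stays in it without an FU visit. On the denominator, SAP 9.1.1 says: "Percentages will be calculated out of the number of subjects in the safety set". SAP 9.1.2 and 9.1.3 use the same base for relationship and severity.
- **What counts as treatment-emergent.** SAP 9.1: "A TEAE is defined as any event not present before exposure to study drug", or one that worsens afterwards. The definition does not cut at TOC or at rescue.
- **What is recorded about follow-up.** SAP 7.2.1: "The duration of study participation (days) is calculated as date of Study Completion/Termination recorded" on the End of Study page, less the first dose date, plus 1. It is summarised by treatment. SAP 7.1.3 tabulates rescue by period. No adverse event table uses either.

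**The concern.** A crude percentage compares the arms fairly when both are watched for about the same time. Here the time a woman is watched depends on whether she was rescued. Rescue follows from poor response, and the design expects poorer response on placebo. Events that begin between TOC and FU therefore have less chance of being recorded on placebo, even if the true risk is the same in both arms. Safety and tolerability versus placebo is a stated secondary objective, and the crude TEAE tables are what the plan offers for it. The participation and rescue summaries would reveal an imbalance but would not correct the percentages. Protocol 16.11 follows known events to an outcome; it does not collect new events after a woman has left.

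**Working it through.** **Inputs from the documents.** Cure 50% v 30%, 2:1 allocation, 244 and 122 women (Protocol 18.1); TOC Day 11, FU Day 25.

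**Check of the plan's own figure.** With pooled variance under the null, placebo n = [1.960·√(0.4333·0.5667·1.5) + 1.2816·√(0.3·0.7 + 0.5·0.5/2)]² / 0.20² = (1.1895 + 0.7418)² / 0.04 = 93.2, so 94. Total 94 + 188 = 282, as stated (power 90.2%). The implied failure rates, 50% and 70%, are therefore those on which the design rests.

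**Assumptions, not in the documents.**
- f is the share of failures rescued by TOC, the same in both arms, from 25% to 100%.
- R is the true 25-day TEAE risk, equal in both arms, from 20% to 40%.
- The design's failure rates apply to the safety set.
- Rescued women are observed to Day 11 and all others to Day 25.

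**Observation time.** Share ending by TOC = failure rate × f. Mean days = 25 − 14 × share.

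| f | Ends by TOC, ibrexafungerp v placebo | Mean days | Difference |
|---|---|---|---|
| 25% | 12.5% v 17.5% | 23.25 v 22.55 | 0.70 |
| 50% | 25% v 35% | 21.5 v 20.1 | 1.40 |
| 100% | 50% v 70% | 18.0 v 15.2 | 2.80 |

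At f = 100% the difference is (FU day − TOC day) × 0.20. That is 4.2 days at the widest spacing (Day 8 and Day 29) and 1.4 at the narrowest (Day 14 and Day 21).

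**Effect on the TEAE percentage.** Let R11 be the risk by Day 11. Recorded percentage = R − share × (R − R11). Artificial gap (ibrexafungerp minus placebo) = 0.20 × f × (R − R11).

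- *Constant hazard:* R11 = 1 − (1 − R)^(11/25), so R − R11 is 10.65, 15.48 and 19.87 points for R = 20%, 30% and 40%.
- *Front-loaded, 90% of first events by Day 11:* R − R11 = 0.1R, or 2, 3 and 4 points.

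| R | f | Gap, constant hazard | Gap, front-loaded |
|---|---|---|---|
| 20% | 25% | 0.53 | 0.10 |
| 30% | 50% | 1.55 | 0.30 |
| 30% | 100% | 3.10 | 0.60 |
| 40% | 100% | 3.97 | 0.80 |

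In 122 placebo women, 0.8 points is about one woman (0.008 × 122 = 1.0) and 4.0 points about five (0.0397 × 122 = 4.8).

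**If f differs by arm.** With fP on placebo and fI on ibrexafungerp, the gap is (0.7·fP − 0.5·fI) × (R − R11). It vanishes at fP = (5/7)·fI and reverses below that. It exceeds the tabulated values if fP is well above fI: at fP = 75%, fI = 25% and R = 30% it is 0.40 × 15.48 = 6.2 points under constant hazard, or 0.40 × 3 = 1.2 front-loaded.

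**Would a rate per subject-day help?** Take R = 30%, f = 50%, front-loaded. Crude: 30 − 0.25 × 3 = 29.25% v 30 − 0.35 × 3 = 28.95%, a placebo/ibrexafungerp ratio of 0.99. Divided by mean participation: 29.25/21.5 = 1.360 v 28.95/20.1 = 1.440, a ratio of 1.06. A 1% distortion becomes about 6% the other way.

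**The case against.** The case for leaving the plan alone is strong on size.

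- **Failure is not rescue.** A residual score of 1 is a clinical failure, but rescue is the investigator's decision, with symptoms of 3 or more given as an example and a negative KOH test weighing against it. A reader might infer that 50% v 70% lose post-TOC observation. The documents do not support that; it is only the upper bound. Nor do they support a common f: in the Phase 2b study (Protocol 7.1) one woman on 600 mg was rescued (27 assessed for cure) against seven on fluconazole (24 assessed), not split at TOC.
- **Events are likely to be early.** Dosing lasts one day, and Phase 2b events at this dose were mainly short gastrointestinal ones. The front-loaded column is the more plausible.
- **The direction is conservative for the drug.** Under-counting placebo makes ibrexafungerp look worse. A reader might infer that the plan flatters ibrexafungerp; on these inputs it does the opposite.
- **The safety analysis is descriptive.** No test is planned on TEAEs. Laboratory tests, vital signs and physical examinations are scheduled only at Screening and TOC, so a missing FU visit leaves them untouched.
- **Post-rescue events.** A reader might infer that the open-ended TEAE definition lets many post-rescue events into the tables. Collection ends at FU, and rescued women leave after the TOC or FU procedures, so little post-rescue time is observed.

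All of this stands and limits the point to a minor one. It does not remove the mechanism: nothing in SAP 9 puts the arms on a common window, and late events in rescued ibrexafungerp women are missed too, which understates absolute risk.

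**Conclusion.** The point holds as a minor one. Length of adverse event observation depends on rescue, and the TEAE percentages take no account of it. If f is common to both arms at 25–100% and the true risk is an equal 20–40%, placebo is under-counted relative to ibrexafungerp by about 0.1–0.8 points if 90% of first events fall by Day 11, and by about 0.5–4.0 points under constant hazard. The true figure depends on rescue rates that the documents do not give, and would be smaller or larger if f differs by arm. Mainly events with onset after TOC are affected.

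A reader might infer that the safety comparison is unsound, or that exposure-adjusted rates are required. Neither follows. The likely distortion is small and against the drug, and with front-loaded events a rate per subject-day would over-correct in the drug's favour. Efficacy results, alpha and sample size are unaffected.

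**What to change.** Keep the planned tables. In SAP 9.1.1:

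1. Add a TEAE summary by SOC and PT limited to onset from first dose through the TOC or early-termination visit, with a second version cut at Study Day 8. Day 8 is the earliest day of the TOC window, so that version gives a common window for every woman seen at a TOC visit in its window. State by arm how many women left before Day 8.
2. Report TEAEs with onset after TOC separately, with the women still under observation after TOC as the denominator. Label the table descriptive, since those women are selected by not having been rescued.
3. Flag events with onset after rescue in the adverse event listing already planned.
4. Do not add an exposure-adjusted rate per subject-day.

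Reconcile Protocol 11.4 and 16.9 so that both say when adverse event collection ends for a woman rescued before FU.

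Cost: SAP wording and one or two extra descriptive tables, from dates and diary data already collected. The downside is a little more output to interpret.

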9.1.2. Relationship of Adverse Events to Study Treatment

A summary of TEAEs by relationship to study treatment will be presented in a table. The investigator will provide an assessment of the relationship of the event to the study treatment. The possible relationships are “Not Related” and “Related”. In the TEAE relationship table, if a subject reports multiple occurrences of the same TEAE, only the most closely related occurrence will be presented. Treatment-emergent AEs that are missing a relationship will be presented in the summary table as “Related” but will be presented in the data listing with a missing relationship. Percentages will be calculated based on the number of subjects in the safety set.

The TEAE data will be categorized and presented by SOC, PT, and relationship in a manner similar to that described in Section 9.1.1.

Treatment-emergent SAEs by relationship to study treatment will also be presented in a table. Treatment-emergent SAEs that are missing a relationship will be presented in the table as “Related” but will be presented in the data listing with a missing relationship.

9.1.3. Severity of Adverse Event

A summary of TEAEs by severity will be presented in a table. The severity that will be presented represents the most extreme severity captured on the CRF page. The possible severities are “Mild”, “Moderate”, and “Severe”.

In the TEAE severity table, if a subject reported multiple occurrences of the same TEAE, only the most severe will be presented. An additional row “Missing” has to be added for the missing severity. Percentages will be calculated out of the number of subjects in the safety set.

The TEAE data will be categorized and presented by SOC, PT, and severity in a manner similar to that described in Section 9.1.1.

Additionally, the TEAE data will be categorized and presented by SOC, PT, severity, and relationship. At each combination level of severity and relationship, a subject is counted once if the subject reported one or more events. Percentages will be calculated out of the number of subjects in the safety set.

Treatment-emergent SAEs by severity will also be presented in a table.

9.1.4. Adverse Events Leading to Treatment Discontinuation

A summary of the TEAEs with an action taken with study treatment of “Drug Withdrawn” will be presented by treatment in a manner similar to that described in Section 9.1.1.

Any TEAEs leading to treatment discontinuation will be presented in a listing for all subjects.

9.1.5. Adverse Events Leading to Study Discontinuation

All subjects who have an AE with the answer to “Caused Study Discontinuation” is “Yes” will be presented in a listing.

9.1.6. Death

All subjects who have an AE with an outcome of “Death Related to Adverse Event” will be presented in a listing.

9.2. Clinical Laboratory Evaluations

Summary tables will be presented for laboratory test results (hematology and blood chemistry) by treatment at Screening and TOC visit for subjects in the safety set.

All relevant clinical laboratory tests in chemistry and hematology will be classified as Low, Normal, and High according to the normal ranges. This categorical data will be summarized in shift tables comparing the extreme results at TOC visit with those at the baseline visit. Extreme post-baseline results will also be summarized. When there are multiple values within a visit for a particular laboratory variable, the worst value will be taken (worst being the smallest value for criteria below a certain threshold or the largest value for criteria above a certain threshold). If a subject has a value below the threshold and above the threshold, the value furthest from the threshold will be chosen.

Plots of average clinical laboratory parameters may be presented.

In data listings, laboratory values will be compared to normal ranges; out-of-range and clinically significant laboratory values will be identified.

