14.7 Safety Laboratory Tests

Safety laboratory tests will be performed by a qualified central laboratory. Samples for safety laboratory tests will be collected at the Screening and the TOC visits and at any unscheduled visit, if needed. If indicated, these may be done more frequently as follow up to a laboratory abnormality.

The following laboratory parameters will be determined:

Hematology

- White blood cell (WBC) count
- Red blood cell (RBC) count
- Platelet count
- Hemoglobin
- Hematocrit

- Differential WBC count will include percentages for lymphocytes, monocytes, eosinophils and basophils, and absolute counts for neutrophils, lymphocytes, atypical lymphocytes, monocytes, eosinophils and basophils.

Blood Chemistry

- Glucose
- Albumin
- Sodium
- Potassium
- Alkaline Phosphatase
- Creatinine
- Total creatine phosphokinase (CPK)
- Aspartate aminotransferase (AST/SGOT)
- Alanine aminotransferase (ALT/SGPT)
- Gamma glutamyl transferase (GGT)
- Bilirubin (total, direct and indirect)
- Total protein

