18.3 Subject Disposition, Discontinuation, and Baseline Data

Subject disposition in terms of the number and percentage of subjects enrolled by site will be tabulated. The number of subjects randomized, number completing the study, and reasons for discontinuation will be summarized by treatment group. Subject demographics and baseline characteristics such as age, race, ethnicity, sex, weight, height, body mass index, region (if applicable) and other relevant parameters will be tabulated by treatment group.

Baseline is defined as the last non-missing assessment prior to the date (and time if appropriate) of the first dose of study drug. Change from baseline is defined as: post-baseline value – baseline value.

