Unless otherwise specified, baseline will be defined as the last non-missing assessment prior to or on the date (and time if appropriate) of the first dose of study drug. Change from baseline is defined as: post-baseline value – baseline value.

The study day will be calculated as follows:

If the assessment date occurs on or after the date of the first dose of study drug:

$$\text{Study day} = \text{assessment date} - \text{first dose date} + 1.$$

If the date of interest occurs before the date of the first dose of study drug:

$$\text{Study day} = \text{assessment date} - \text{first dose date}$$

There is no study day 0.

All analyses will be conducted using SAS Version 9.3 or higher. All statistical tests will be two-sided and interpreted at a 5% significance level.

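### SAP 9.2 keeps only one of two opposite laboratory abnormalities, chosen by an undefined distance, and its shift-table baseline can be read against SAP Section 4

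*SAP*

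**What the plan says.** SAP 9.2 classes each haematology and chemistry result as Low, Normal or High against the normal range. It presents "shift tables comparing the extreme results at TOC visit with those at the baseline visit" and, in addition, a summary of extreme results after baseline. Two selection rules follow.

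- For repeats: "When there are multiple values within a visit for a particular laboratory variable, the worst value will be taken", with "worst being the smallest value for criteria below a certain threshold or the largest value for criteria above a certain threshold".
- For results in both directions: "If a subject has a value below the threshold and above the threshold, the value furthest from the threshold will be chosen".

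On baseline, SAP Section 4 says: "Unless otherwise specified, baseline will be defined as the last non-missing assessment prior to or on the date" of first dose. Protocol 18.3 says: "Baseline is defined as the last non-missing assessment prior to the date (and time if appropriate) of the first dose of study drug". Both take the last non-missing value.

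Protocol 14.7 and the visit schedule plan one safety sample before dosing (Screening) and one after (TOC), plus unscheduled samples if needed. Protocol 14.7 adds that "these may be done more frequently as follow up to a laboratory abnormality".

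**The concern.** Two parts of SAP 9.2 can misplace a result in the by-arm laboratory tables.

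The first is the rule for results in both directions. It speaks of a single threshold, but the classification has two limits. It does not say whether distance is in raw units or relative to a limit. Because it is worded for a subject and not for a visit, it can also reach the post-baseline extremes, where TOC and unscheduled samples may be pooled. One of two real abnormalities is discarded, and two programmers following the text could discard different ones.

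The second is the baseline for the shift tables. The comparison of extremes at TOC with those at the baseline visit, together with a worst-value rule that is not limited to post-baseline visits, suggests that the baseline category is also a worst value. SAP Section 4 gives way where something else is specified, so SAP 9.2 could be taken as an override.

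At stake is the by-arm description of laboratory safety in women re-tested because something was abnormal. Efficacy, sample size and type I error are not involved.

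**Working it through.** The plan gives no figure to reproduce here. The check applies the rules to example values. The documents give no reference ranges, so all ranges and values below are assumptions.

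**Rule for two directions.** Let L and U be the lower and upper limits, a the low value and b the high value. Four readings of the distance are possible:

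1. From each value's own limit: L − a against b − U.
2. From the lower limit only: L − a against b − L.
3. From the upper limit only: U − a against b − U.
4. As a fraction of the own limit: (L − a)/L against (b − U)/U.

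White cells, range 4 to 11, values 2.0 and 14.0:

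- Reading 1: 4 − 2 = 2 against 14 − 11 = 3. High is kept.
- Reading 2: 2 against 14 − 4 = 10. High is kept.
- Reading 3: 11 − 2 = 9 against 3. Low is kept.
- Reading 4: 2/4 = 0.50 against 3/11 = 0.27. Low is kept.

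The same steps for three other tests give:

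| Test (assumed range) | Values | Own limit | Lower limit | Upper limit | Fraction of own limit |
|---|---|---|---|---|---|
| Platelets (150–400) | 60, 520 | 90 v 120: High | 90 v 370: High | 340 v 120: Low | 0.60 v 0.30: Low |
| Glucose (70–140) | 45, 180 | 25 v 40: High | 25 v 110: High | 95 v 40: Low | 0.36 v 0.29: Low |
| Potassium (3.5–5.0) | 2.8, 5.6 | 0.7 v 0.6: Low | 0.7 v 2.1: High | 2.2 v 0.6: Low | 0.20 v 0.12: Low |

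In every example the result turns on the undefined term, and either direction can be lost.

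**Baseline.** Take an assumed upper limit of 40 for ALT, and compare the last pre-dose value with the worst pre-dose value, supposing that both pre-dose samples count as the baseline visit:

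| Pre-dose values, in order | Post-dose | Last value as baseline | Worst value as baseline |
|---|---|---|---|
| 48, 32 | 55 | Normal to High | High to High |
| 32 | 55 | Normal to High | Normal to High |
| 32, 48 | 55 | High to High | High to High |
| 48, 32 | 32 | Normal to Normal | High to Normal |

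In these examples the two baselines differ only when a pre-dose repeat exists and an earlier value is worse than the last. The first row hides a new abnormality. The fourth creates a shift that the last-value baseline would not show.

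**The case against.** The strongest reply is that this hardly ever matters and is visible elsewhere. Much of that stands.

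- **Rarity.** One sample is scheduled on each side of dosing. The tie rule needs the same woman to be below range and above range on the same test, in different samples. The baseline problem needs a pre-dose repeat that improved. Safety samples go to a central laboratory, Screening is at most a few days before dosing, and a redraw at an unscheduled visit is not a second value within one visit.
- **Other displays.** SAP 9.2 also summarises results at Screening and TOC, and its listings flag out-of-range and clinically significant values. Protocol 16.1 makes a clinically significant laboratory abnormality an adverse event, so a treatment-emergent one enters the tables of SAP 9.1. SAP 9.2.2 counts liver elevations at any post-baseline visit.
- **Directions already separated.** The definition of worst treats low and high criteria separately. The tie sentence comes after it, however, and reduces the two to one value. No separate lowest and highest tables are stated.

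The reply limits the harm but does not repair the rule. Listings give no by-arm comparison, and low blood counts have no summary like the one for liver tests.

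Four stronger readings are tempting, and the documents do not support them:

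- *The SAP uses the worst pre-dose value as baseline.* It nowhere says so. SAP Section 4 and Protocol 18.3 say last non-missing. SAP 9.2 only permits a contrary reading, and then for values within a visit.
- *The rule systematically loses low counts.* In raw distance from each value's own limit, any high above L + U outranks even a low of zero (for platelets, 150 + 400 = 550). The SAP does not state that scale. Potassium keeps the low value even on it, and the other readings can drop the high value.
- *The rules can only remove abnormalities.* The tie rule still leaves the woman abnormal. The worst value at TOC keeps a High that normalised on repeat, and a worst-value baseline can create shifts.
- *A number of affected women can be given.* The documents state no re-test rate. An assumed rate applied to 366 women would count women re-tested, not women misclassified.

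**Conclusion.** Wrong as written, but minor.

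The tie rule is a stated rule, not a missing detail. When it operates, it leaves one real abnormality out of the by-arm table, and which one depends on a term the SAP does not define. This conclusion does not depend on the assumed ranges, which only illustrate it.

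The baseline part is weaker. It is an unreconciled conflict between SAP 9.2, on one natural reading, and the last-non-missing definition in SAP Section 4 and Protocol 18.3. It is not a declared change of baseline. On that reading a new post-dose abnormality can appear as no shift, and some spurious shifts can also arise.

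Few women, possibly none, will be affected. The number cannot be computed from the documents.

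**What to change.** In SAP 9.2, before unblinding:

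- **(a)** Replace the sentence that picks one value by distance. Summarise each woman's lowest and highest post-baseline value separately, with a shift to lowest and a shift to highest, so that a woman with both abnormalities counts in both.
- **(b)** State that the worst-value rule applies to post-baseline values only, and that the baseline for laboratory shifts is the last non-missing pre-dose value as in SAP Section 4.

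The cost is a short edit and one extra shift table per laboratory panel. No new data are needed. A woman may then appear in both a low and a high row, which a table footnote can say.
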